## 3 Study Objectives and Endpoints

### 3.1 Study Objectives

#### 3.1.1 Primary Objectives, Phase 2

**Safety:** To evaluate the safety profile of a single intramuscular dose of IVACFLU-S seasonal trivalent inactivated split virion influenza vaccine in adults, 18 to 60 years of age.

#### 3.1.2 Primary Objectives, Phase 3

**Safety:** To evaluate the safety profile of a single intramuscular dose of IVACFLU-S seasonal trivalent split virion, inactivated influenza vaccine in adults, 18 to 60 years of age.

**Immunogenicity:** To evaluate the immune response at Day 22 to each of the three vaccine antigens after a single intramuscular dose of IVACFLU-S seasonal trivalent split virion, inactivated influenza vaccine in adults, 18 to 45 and 46 to 60 years of age.

#### 3.1.3 Secondary Objective, Phase 3

**Immunogenicity:** To evaluate the immune response at Day 22 to each of the three vaccine antigens after a single dose of IVACFLU-S seasonal trivalent split virion, inactivated influenza vaccine in adults with and without pre-existing Hemagglutination Inhibition (HAI) antibody

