## 6. GENERAL CONSIDERATIONS

By-subject data listings, summary tables, figures and statistical tests will be performed using SAS® Version 9.4 or higher.

All clinical data, including laboratory and clinical data from an internal database will be provided as raw datasets. CDISC SDTM 3.2 compliant SAS datasets will then be generated. Coding of AEs and current medical conditions will be included in the SDTM datasets.

Appropriate SAS programs will be prepared and validated according to QuintilesIMS standard operating procedures.

The following descriptive statistics will be presented in summary tables:

- Continuous variables: Number (observed cases), mean, median, standard deviation (SD), minimum, and maximum

---

Document:	\\EEDC-NAS01A\Biosdata\Path\IVACFLU-S\IYA06804\Biostatistics		
	Documentation\SAP\IVACFLU-S-0203_SAP_Draft v1.0		
Author:	[name]	Version Number:	1.0
		Version Date:	[11AUG2017]
Template No:	CS_TP_BS016 Revision 4	Reference:	CS_WI_BS005
Effective Date:	01Apr2016		

- Categorical variables: Summarized by treatment group using frequency tables (frequency [n] and percentage [%]). Percentages will be calculated relative to the total number of subjects in the relevant analysis set with data available, if not otherwise specified.

Two-sided exact 95% confidence intervals (CIs) will be presented unless otherwise specified.

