## 7.5 EXAMINATION OF SUBGROUPS

1. All safety and immunogenicity analyses will be conducted for subgroups of age category i.e., 18-45 and 46-60.
2. Analysis of secondary immunogenicity endpoints, Phase 3, will be conducted for subgroups of pre-vaccination HAI antibody titer i.e., <1:10 or  $\geq$  1:10 and subgroups of age category i.e., 18-45 and 46-60.

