## 16.2.2 SECONDARY IMMUNOGENICITY ENDPOINTS

- A. Number and percentage of subjects by age groups (18-45, 46-60) who develop at least a four-fold increase in HAI antibody titer to each of the vaccine antigens post vaccination measured on Day 22 by pre-vaccination HAI antibody titer of  $<1:10$  or  $\geq 1:10$ .
- B. Geometric mean titers (GMTs) of serum HAI antibodies pre- (Day 1) and post vaccination (Day 22) by age groups (18-45, 46-60) for each of the 3 vaccine antigens by prevaccination HAI antibody titer of  $<1:10$  or  $\geq 1:10$ .
- C. Geometric mean fold rises (GMFRs) of serum HAI antibodies (post vaccination/prevaccination) by age groups (18-45, 46-60) for each of the 3 vaccine antigens by prevaccination HAI antibody titer of  $<1:10$  or  $\geq 1:10$ .

The following endpoints will be analyzed by age group:

1. For each treatment group, the number and percentage of subjects with a serum HAI antibody titer  $\geq 1:40$  to each of the 3 vaccine components measured on Day 22 post vaccination, will be presented along with two-sided exact 95% CIs using Clopper-Pearson method.
2. For each treatment group, the number and percentage of subjects with seroconversion against each of the 3 vaccine antigens post-vaccination will be presented along with two-sided exact 95% CIs using Clopper-Pearson method.
3. GMTs of serum HAI antibodies for each of the 3 antigens will be summarized at each time point (Day 1 and Day 22) by treatment group along with the corresponding two-sided 95% CIs, by exponentiating the corresponding log-transformed means and their 95% CIs.
4. GMFRs of serum (HAI) antibodies (post-vaccination / pre-vaccination) for each of the 3 antigens will be summarized by treatment group along with the corresponding two-sided 95% CIs, by exponentiating the corresponding difference in log-transformed means between post-vaccination and pre-vaccination antibodies and their 95% CIs obtained via paired t-test method.

The following endpoints will be analyzed by age group and pre-vaccination HAI antibody titer of  $<1:10$  or  $\geq 1:10$ :

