1. For each treatment group, the number and percentage of subjects who develop at least a four-fold increase in HAI antibody titer to each of the 3 vaccine antigens measured on Day 22 post vaccination, will be presented along with two-sided exact 95% CIs using Clopper-Pearson method. (Please refer to [Appendix 2](#) for sample SAS code for 95% confidence interval for single proportion using Exact Clopper-Pearson method).
2. GMTs of serum HAI antibodies for each of the 3 antigens will be summarized at each time point (Day 1 and Day 22) by treatment group along with the corresponding two-sided 95% CIs, by exponentiating the corresponding log-transformed means and their 95% CIs.

---

Document:	\\EEDC-NAS01A\Biosdata\Path\IVACFLU-S\IYA06804\Biostatistics		
	Documentation\SAP\IVACFLU-S-0203_SAP_Draft v1.0		
Author:	[name]	Version Number:	1.0
		Version Date:	[11AUG2017]
Template No:	CS_TP_BS016 Revision 4	Reference:	CS_WI_BS005
Effective Date:	01Apr2016		

3. GMFRs of serum (HAI) antibodies (post-vaccination / pre-vaccination) for each of the 3 antigens will be summarized by treatment group along with the corresponding two-sided 95% CIs, by exponentiating the corresponding difference in log-transformed means between post-vaccination and pre-vaccination antibodies and their 95% CIs obtained via paired t-test method.

Subject wise listing will be generated.

Graphical representation of the data will be as follows:

1. Geometric mean HAI titer for each of the 3 antigens at Days 1 and 22 will be plotted by vaccine group separately for each age group.
2. Reverse Cumulative Distribution (RCD) plot will show reverse cumulative percentages for HAI titer for each of the 3 antigens at Day 1 and Day 22 by vaccine group and by age group.

The immunogenicity analyses will be performed using PP population.

All immunogenicity analyses will also be conducted using FA population as supportive analyses.

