### Sample SAS code for 95% confidence interval for single proportion using Exact Clopper-Pearson method:

```
proc freq data =combb order=data;
by _name_ atptn atpt mord parcat3n parcat3 cat;
tables pflg / binomial (exact) alpha = 0.05;
weight cnt/zero;
ods output BinomialCLs = bin_ci;
run;
```

## APPENDIX 3

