Document:	\\EEDC-NAS01A\Biosdata\Path\IVACFLU-S\IYA06804\Biostatistics \Documentation\SAP\IVACFLU-S-0203_Mock_Tables_V1.0		
Author:	[name]	Version Number:	1.0
		Version Date:	11AUG 2017]

Template No: CS\_TP\_BS016 Revision 4  
Effective Date: 01Apr2016

Reference: CS\_WI\_BS005

TABLE AND LISTING MOCK SHELL

Same layout as for 14.2.1.7

Table 14.2.1.9  
Immune Response Rates and 95% Confidence Intervals for the Hemagglutination Inhibition (HAI) Titers by age group and pre-vaccination titer group -four-fold rise - Per-protocol population

Age Group: <Overall> <18-45> <46-60>				
Titers	Pre-vaccination titer group	Day	Vaccine (N=xx)	Placebo (N=xx)
< <1:10 > < ≥1:10 >				
A/H1N1	<1:10	Four-fold increase		
		n	xx	xx
		n/N(%)	xx.x	xx.x
		95% CI	[xx.xx, xx.xx]	[xx.xx, xx.xx]
		Day 22		
A/H1N1	≥1:10	Four-fold increase		
		n	xx	xx
		n/N(%)	xx.x	xx.x
		95% CI	[xx.xx, xx.xx]	[xx.xx, xx.xx]
		Day 22		
A/H3N2				
B				

Sera samples were collected in phase 3 study at one site (Ben Luc).  
N- Total number of subjects in each group; n - Total number of subjects with four-fold increase on Day 22.  
Percentages were based on the total number of subjects in each vaccine group (N).  
95% confidence interval for single proportion is calculated using Exact Clopper-Pearson method.  
Pre-vaccination (Day 1) value is considered as baseline.  
Source: Listing 16.2.6.1

Document: \\EEDC-NAS01A\Biosdata\Path\IVACFLU-S\IYA06804\Biostatistics \Documentation\SAP\IVACFLU-S-0203\_Mock\_Tables\_V1.0  
Author: [name]  
Version Number:  
Version Date:

1.0  
11AUG 2017]

Template No: CS\_TP\_BS016 Revision 4  
Effective Date: 01Apr2016

Reference: CS\_WI\_BS005

Copyright © 2009, 2010, 2012, 2016 Quintiles Transnational Corp. All rights reserved.  
The contents of this document are confidential and proprietary to Quintiles Transnational Corp. Unauthorized use, disclosure or reproduction is strictly prohibited.

TABLE AND LISTING MOCK SHELL

Programming note: Repeat the shell for all the three age groups and also repeat H3N2 and B for both the pre-vaccination groups i.e., <1:10, ≥1:10 as presented for H1N1 in the same table.

Table 14.2.1.10  
Immune Response Rates and 95% Confidence Intervals for the Hemagglutination Inhibition (HAI) Titers by age group and pre-vaccination titer group - four-fold rise - Full Analysis population

Same layout as for 14.2.1.9

Table 14.2.1.11  

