Author: [name]  
Version Number:  
Version Date:

1.0  
11AUG 2017]

Template No: CS\_TP\_BS016 Revision 4  
Effective Date: 01Apr2016

Reference: CS\_WI\_BS005

TABLE AND LISTING MOCK SHELL

---

H3N2  
B

Sera samples were collected in phase 3 study at one site (Ben Luc).  
 N- Total number of subjects in each age group; n - Total number of subjects with the titer measurements at both Day 1 and Day 22.  
 The confidence intervals were constructed using t distribution.  
 Pre-vaccination (Day 1) value is considered as baseline.  
 Source: Listing 16.2.6.1

Programming note: Repeat the shell for all the three age groups and also repeat H3N2 and B for both the pre-vaccination groups i.e., <1:10, >1:10 as presented for H1N1 in the same table.

Table 14.2.1.14  
 Geometric Mean Fold Rise (GMFR) for the Hemagglutination Inhibition (HAI) Titers by age group and pre-vaccination titer group  
 Full Analysis population

Same layout as for 14.2.1.13

---

Document:	\\EEDC-NAS01A\Biosdata\Path\IVACFLU-S\IYA06804\Biostatistics \Documentation\SAP\IVACFLU-S-0203_Mock_Tables_V1.0		
Author:	[name]	Version Number:	1.0
		Version Date:	11AUG 2017]
Template No:	CS_TP_BS016 Revision 4	Reference:	CS_WI_BS005
Effective Date:	01Apr2016		

Figure 14.2.1.1  
Reverse cumulative distribution curve for Hemagglutination Inhibition (HAI titer)- Age group [18-45] - Per-protocol population

[figure not shown]
---

Document:	\\EEDC-NAS01A\Biosdata\Path\IVACFLU-S\IYA06804\Biostatistics \Documentation\SAP\IVACFLU-S-0203_Mock_Tables_V1.0	Version Number:	1.0
Author:	[name]	Version Date:	11AUG 2017]
Template No:	CS_TP_BS016 Revision 4	Reference:	CS_WI_BS005
Effective Date:	01Apr2016		

Copyright © 2009, 2010, 2012, 2016 Quintiles Transnational Corp. All rights reserved.  
The contents of this document are confidential and proprietary to Quintiles Transnational Corp. Unauthorized use, disclosure or reproduction is strictly prohibited.

TABLE AND LISTING MOCK SHELL

Programming note: This graph is to be generated for all the three strains, each strain per page, on Day 1 and Day 22 in the same page. i.e., display H1N1 for both Day 1 and Day 22 in the same page. Repeat H3N2 and B as done for H1N1. All these to be generated in the same figure.

Document: \\EEDC-NAS01A\Biosdata\Path\IVACFLU-S\IYA06804\Biostatistics \Documentation\SAP\IVACFLU-S-0203\_Mock\_Tables\_V1.0

Author: [name]

Version Number:

1.0

Version Date:

11AUG 2017]

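### Mock shells 14.2.1.9 and 14.2.1.10 base four-fold-rise percentages for each pre-vaccination titer stratum on the whole treatment group, not on the stratum

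*Combined protocol and SAP*

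**What the plan says.** The only secondary objective (protocol 3.1.3) is the Day 22 immune response "in adults with and without pre-existing Hemagglutination Inhibition (HAI) antibody". Endpoint A addresses it with a response rate.

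SAP 7.5 treats baseline titer as a subgroup factor: "Analysis of secondary immunogenicity endpoints, Phase 3, will be conducted for subgroups of pre-vaccination HAI antibody titer". SAP 16.2.2 introduces the stratified analyses with "The following endpoints will be analyzed by age group and pre-vaccination HAI antibody titer of" <1:10 or ≥1:10. The first item there is the "number and percentage of subjects who develop at least a four-fold increase in HAI antibody titer to each of the 3 vaccine antigens", with exact Clopper-Pearson intervals. Neither section names a denominator.

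The denominator appears in the mock shells. In Table 14.2.1.9 each strain has two rows, one per titer stratum, under a single Vaccine N and a single Placebo N. The rows show n, n/N (%) and the 95% CI, where n counts responders only. The footnote reads: "Percentages were based on the total number of subjects in each vaccine group (N". No row, column or footnote gives the number of subjects in a stratum. Table 14.2.1.10 (Full Analysis population) takes over the same layout.

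**The concern.** A response rate in a subgroup needs the subgroup as its denominator. With the arm's N below the line, the printed figure is the response rate multiplied by the stratum's share of the arm, and the two rows add up to the overall four-fold-rise rate. The table would then mix how well each stratum responds with how common it is. The comparison of people with and without pre-existing antibody could be distorted or reversed, and the exact interval would rest on the wrong sample size.

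**Working it through.** **Method check.** The Clopper-Pearson limits for x of n are the 2.5% quantile of Beta(x, n−x+1) and the 97.5% quantile of Beta(x+1, n−x). Applied to SAP Table 4 (protocol Table 18), this reproduces all seven rows to within 0.1 point, for example 80/100 gives 70.8–87.3% and 50/100 gives 39.8–60.2%. The documents give no figure for the stratified table itself.

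**Inputs.** N = 100 evaluable vaccinees per age group (SAP 16.1) and 20 placebo recipients per age group (protocol 4.1). The documents do not give the share of subjects below 1:10, so the stratum splits and response rates below are assumptions.

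**Identity.** With x responders in a stratum of size m, the shell prints x/N = (x/m) × (m/N). The intended quantity is x/m.

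**Equal response of 80% in every stratum, N = 100:**

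| Stratum size m | Responders x | Shell: x/100 (95% CI) | Correct: x/m (95% CI) |
|---|---|---|---|
| 20 | 16 | 16% (9.4–24.7) | 80% (56.3–94.3) |
| 30 | 24 | 24% (16.0–33.6) | 80% (61.4–92.3) |
| 50 | 40 | 40% (30.3–50.3) | 80% (66.3–90.0) |
| 70 | 56 | 56% (45.7–65.9) | 80% (68.7–88.6) |
| 80 | 64 | 64% (53.8–73.4) | 80% (69.6–88.1) |

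With a 20/80 or a 30/70 split, two strata with the same response rate would print with non-overlapping intervals.

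**Reversal.** Assume true rates of 90% (<1:10) and 70% (≥1:10) and a 30/70 split. Then 0.90 × 30 = 27 and 0.70 × 70 = 49, so the shell prints 27% and 49%. At these rates the order reverses whenever the <1:10 share s satisfies 0.90s < 0.70(1−s), that is s < 0.70/1.60 = 43.75%.

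**Placebo.** With N = 20 and an assumed stratum of 6, no responders gives an upper limit of 16.8% on 0/20 but 45.9% on 0/6.

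**Phase 1 data (protocol 2.1.6).**
- Of 16 vaccinees with baseline H3N2 titer ≥1:40, 12 had a four-fold rise. Within the stratum that is 12/16 = 75.0% (47.6–92.7). On all 30 it is 12/30 = 40.0% (22.7–59.4). This uses a 1:40 cut, so it is only illustrative.
- Those 16 of 30 (53.3%) were necessarily also ≥1:10. If that baseline carried over, the H3N2 <1:10 row could not exceed 1 − 16/30 = 46.7% even if every member responded. The same bound for H1N1 (1 − 5/30 = 83.3%) and B (1 − 3/30 = 90.0%) is weak.

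**Does another part of the plan override the footnote?**
- SAP 6 sets a default: "Percentages will be calculated relative to the total number of subjects in the relevant analysis set with data available, if not otherwise specified". It refers to the analysis set, not the stratum, and gives way to a specific rule such as the shell's.
- The sample code in SAP Appendix 2 runs "by _name_ atptn atpt mord parcat3n parcat3 cat". These variables are not defined, so it cannot be established that titer stratum is among them.
- The companion fold-rise shell, Table 14.2.1.13, prints for each strain and stratum an n defined as "Total number of subjects with the titer measurements at both Day 1 and Day 22". Table 14.2.1.9 has no such count.

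**The case against.** The best counter-reading is that the wrong denominator was never intended. Just above the quoted footnote, the shell defines N by group, where the other immunogenicity table shells say age group, and this table's row heading is the titer group. The percentage footnote also appears in the unstratified Tables 14.2.1.1 and 14.2.1.3, where the stratum problem does not arise, so it may simply have been carried over. Appendix 2, which SAP 16.2.2 cites for this item, uses BY-processing, and that would give within-cell denominators if stratum were a BY variable. This plausibly explains how the line got there, but it does not rescue the shell. The footnote ties N to the vaccine group, and one header N cannot serve two strata whose sizes differ by strain.

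Three limits do stand:
- The footnote on intervals names only the method, so a CI based on N is an inference from n/N being the only proportion shown.
- The worked splits and rates are assumed. The Phase 1 bound comes from 30 vaccinees aged 18–45 and a different H3N2 strain.
- The endpoint is descriptive and is not a licensure criterion. The stratified GMT and GMFR tables are unaffected, and a reader could divide n by the paired count in Table 14.2.1.13 and recompute the interval. The printed percentage and interval would still be wrong.

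**Conclusion.** The concern holds: the denominator rule in Tables 14.2.1.9 and 14.2.1.10 is wrong as written and conflicts with the within-stratum analysis in the SAP. The printed rate is too low by a factor equal to the stratum's share of the arm. An 80% response would appear as anything from 16% to 64% as that share runs from 20% to 80%. The factor follows from the shell alone; the particular figures depend on the assumed shares and rates. The error is confined to secondary endpoint A and should be corrected before the tables are programmed. The primary seroconversion and seroprotection tables do not have this problem.

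**What to change.** In both shells, add a row for each arm, age group, strain and pre-vaccination stratum giving m, the number of subjects with both Day 1 and Day 22 titers. Report n/m (%) and compute the exact interval on m. Replace the footnote with: *Percentages are based on the number of subjects in the treatment, age and pre-vaccination titer group with Day 1 and Day 22 titers (m).* State the same denominator in SAP 16.2.2. Leave the four-fold-rise definition as the protocol has it.

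The cost is one footnote, one added row in two shells, one SAP sentence and the matching programming, with no new data. Intervals will usually be wider because they rest on the true, smaller stratum size.

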## 17.5 VITAL SIGNS

Vital sign measurements include body temperature (oral), blood pressure (systolic and diastolic) and heart rate collected at Screening and Day 8 of the study.

The vital signs measurements, including abnormalities (grading for body temperature and blood pressure) and heart rate associated along with clinical significance (Yes/No) will be presented in the listings.

The following summaries will be provided for vital signs data:

- Actual and change from Baseline to Day 8
- Actual and change from Baseline to Day 8 by grade
- Shift from Baseline to Day 8 by grade
- Number and percentage of subjects by clinical significance
- Number and percentage of subjects shift from Baseline to Day 8 by clinical significance

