### Targeted Physical Examination

The Targeted Physical Examination (PE) focuses on symptoms reported by the participant and the presence or absence of local and systemic reactogenicity. If no symptoms are reported by the participant, the Targeted PE does not need to be performed. The exam will be made by a clinician on D1 (only if D1 is on a different day from S1) and Day 8. Evaluation must be made prior to administration of injection of study product if done on Day 1.

Subject-wise listing of the data will be presented.

Summary of Shift from baseline to Day 8 by clinically significant abnormal physical examination will also be presented.

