 The contents of this document are confidential and proprietary to Quintiles Transnational Corp. Unauthorized use, disclosure or reproduction is strictly prohibited.

TABLE AND LISTING MOCK SHELL

Table 14.3.6.2  
Shift from Baseline to Day 8 of Vital Signs by Grade  
Full Analysis Population

Age Group: <Overall> <18-45> <46-60>

Day 8

Parameter (Unit)	Baseline	Vaccine (N=xx) n (%)				Placebo (N=xx) n (%)				Total (N=xx) n (%)			
		1	2	3	4	1	2	3	4	1	2	3	4
Body Temperature (Oral) (°C) *	1	Xx (xx.xx)	Xx (xx.xx)	Xx (xx.xx)	Xx (xx.xx)	Xx (xx.xx)	Xx (xx.xx)	Xx (xx.xx)	Xx (xx.xx)	Xx (xx.xx)	Xx (xx.xx)	Xx (xx.xx)	Xx (xx.xx)
	2	Xx (xx.xx)	Xx (xx.xx)	Xx (xx.xx)	Xx (xx.xx)	Xx (xx.xx)	Xx (xx.xx)	Xx (xx.xx)	Xx (xx.xx)	Xx (xx.xx)	Xx (xx.xx)	Xx (xx.xx)	Xx (xx.xx)
	3												
	4												

Data is based on the combined phases 2 and 3, pooled across study sites.

N= Total number of subjects in the relevant population per by-group stratification level. n= Number of subjects with available response under each group at both visit. % = Calculated relative to the total number of subjects have measurable assessment for analysis in each group at both time points.

Grades: 1- Mild; 2 - Moderate; 3 - Severe; 4 - Life-Threatening;

\*Body temperature collected in vital signs.

Source Data: Listing 16.2.8.2

Document: \\EEDC-NAS01A\Biosdata\Path\IVACFLU-S\IYA06804\Biostatistics \Documentation\SAP\IVACFLU-S-0203\_Mock\_Tables\_V1.0  
Author: [name]  
Version Number: 1.0  
Version Date: 11AUG 2017]

Template No: CS\_TP\_BS016 Revision 4  
Effective Date: 01Apr2016

Reference: CS\_WI\_BS005

Copyright © 2009, 2010, 2012, 2016 Quintiles Transnational Corp. All rights reserved.

The contents of this document are confidential and proprietary to Quintiles Transnational Corp. Unauthorized use, disclosure or reproduction is strictly prohibited.

TABLE AND LISTING MOCK SHELL

---

Programming Note: Summarize for the parameters systolic blood pressure (mmHg), diastolic blood pressure (mmHg) and pulse rate (beats/min).

---

Document:	\\EEDC-NAS01A\Biosdata\Path\IVACFLU-S\IYA06804\Biostatistics \Documentation\SAP\IVACFLU-S-0203_Mock_Tables_V1.0		
Author:	[name]	Version Number:	1.0
		Version Date:	11AUG 2017]
Template No:	CS_TP_BS016 Revision 4	Reference:	CS_WI_BS005
Effective Date:	01Apr2016		

Copyright © 2009, 2010, 2012, 2016 Quintiles Transnational Corp. All rights reserved.  

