The contents of this document are confidential and proprietary to Quintiles Transnational Corp. Unauthorized use, disclosure or reproduction is strictly prohibited.

TABLE AND LISTING MOCK SHELL

Table 14.3.6.3  
Shift from Baseline to Day 8 of Clinically Significant Vital Signs Parameter  
Full Analysis Population

Age Group: <Overall> <18-45> <46-60>		Day 8					
Parameter (Unit)	Baseline	Vaccine (N=xx) n (%)			Placebo (N=xx) n (%)		
		Normal	Abnormal, NCS	Abnormal, CS	Normal	Abnormal, NCS	Abnormal, CS
Body Temperature (°C)	Normal	xx (xx.x)	xx (xx.x)	xx (xx.x)	xx (xx.x)	xx (xx.x)	xx (xx.x)
	Abnormal, NCS	xx (xx.x)	xx (xx.x)	xx (xx.x)	xx (xx.x)	xx (xx.x)	xx (xx.x)
	Abnormal, CS	xx (xx.x)	xx (xx.x)	xx (xx.x)	xx (xx.x)	xx (xx.x)	xx (xx.x)

...  
Data is based on the combined phases 2 and 3, pooled across study sites.  
CS: Clinically Significant; NCS: Not Clinically Significant;  
N= Total number of subjects in the relevant population per by-group stratification level, n= Number of subjects with available response under each group at both time point, % = Calculated relative to the total number of subjects have measurable assessment for analysis in each group at both visit  
Percentages were based on the total number of subjects have measurable assessment for analysis in each group.  
Source Data: Listing 16.2.8.2  
Programming Note: Add Total Column also i.e., in addition to Vaccine and Placebo.  
Summarize for the parameters systolic blood pressure (mmHg), diastolic blood pressure (mmHg) and pulse rate (beats/min).

Document:	\\EEDC-NAS01A\Biosdata\Path\IVACFLU-S\IYA06804\Biostatistics \Documentation\SAP\IVACFLU-S-0203_Mock_Tables_V1.0		
Author:	[name]	Version Number:	1.0
		Version Date:	11AUG 2017]
Template No:	CS_TP_BS016 Revision 4	Reference:	CS_WI_BS005
Effective Date:	01Apr2016		

TABLE AND LISTING MOCK SHELL

Table 14.3.7.1  
Shift from Baseline to Day 8 by Clinically Significant Abnormal Physical Examination  
Full Analysis Population

Age Group: <Overall> <18-45> <46-60>

Area/ System	Baseline	Day 8			
		Vaccine (N=xx) n (%)		Placebo (N=xx) n (%)	
		Abnormal, NCS	Abnormal, CS	Abnormal, NCS	Abnormal, CS
xxxxxxxxx	Abnormal, NCS	xx (xx.x)	xx (xx.x)	xx (xx.x)	xx (xx.x)
	Abnormal, CS	xx (xx.x)	xx (xx.x)	xx (xx.x)	xx (xx.x)

Data is based on the combined phases 2 and 3, pooled across study sites.

CS: Clinically Significant; NCS: Not Clinically Significant;

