N= Total number of subjects in the relevant population per by-group stratification level, n= Number of subjects with available response under each group at both time points, % = Calculated relative to the total number of subjects have measurable assessment for analysis in each group at both visit  
Programming Note: Add Total Column also i.e., in addition to Vaccine and Placebo.

Source Data: Listing 16.2.8.3

Document: \\EEDC-NAS01A\Biosdata\Path\IVACFLU-S\YA06804\Biostatistics \Documentation\SAP\IVACFLU-S-0203\_Mock\_Tables\_V1.0

Author: [name]

Version Number:

1.0

Version Date:

11AUG 2017]

Template No: CS\_TP\_BS016 Revision 4

Reference: CS\_WI\_BS005

Effective Date: 01Apr2016

Copyright © 2009, 2010, 2012, 2016 Quintiles Transnational Corp. All rights reserved.

The contents of this document are confidential and proprietary to Quintiles Transnational Corp. Unauthorized use, disclosure or reproduction is strictly prohibited.

ANNOTATED SHELLS

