	

• Life-threatening blood pressure is defined to be grade 3 elevated blood pressure along with one of the following symptoms which require hospitalization indicated, e.g., headache, breathing difficulty, blurred vision, chest pain.

Pulse rate	

• Normal: 60 - 90 beats/min.

• Abnormal - NCS: 55 - < 60 beats/min or 91-100 beats/min.

• Abnormal - CS: < 55 beats/min, or > 100 beats/min and there are clinical signs or symptoms which need intervention or there are abnormal cardiac findings after examination. For this case, the Investigator should record the reason for his assessment in the subject binder.

• Note: There is no grading scale for pulse rate.

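### Two Day 8 safety shift shells have no category for participants without an abnormality, so they cannot show a finding appearing or resolving

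*Combined protocol and SAP*

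**What the plan says.** SAP 17.5 lists, among the vital-sign summaries, "Shift from Baseline to Day 8 by grade". SAP 17.6 plans a listing of physical examination data and adds: "Summary of Shift from baseline to Day 8 by clinically significant abnormal physical examination will also be presented". Neither section limits the shift to participants who were abnormal at baseline.

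The mock shells turn these into tables:

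- **Table 14.3.6.2**, "Shift from Baseline to Day 8 of Vital Signs by Grade", has baseline rows 1, 2, 3, 4 and Day 8 columns 1, 2, 3, 4 for vaccine, placebo and total. Its legend reads "Grades: 1- Mild; 2 - Moderate; 3 - Severe; 4 - Life-Threatening". A programming note extends the layout to systolic pressure, diastolic pressure and pulse rate.
- **Table 14.3.7.1**, "Shift from Baseline to Day 8 by Clinically Significant Abnormal Physical Examination", has baseline rows Abnormal NCS and Abnormal CS, and the same two columns at Day 8. Its only programming note is "Programming Note: Add Total Column also i.e., in addition to Vaccine and Placebo".
- **Table 14.3.6.3**, "Shift from Baseline to Day 8 of Clinically Significant Vital Signs Parameter", has Normal, Abnormal NCS and Abnormal CS on both axes.

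The criteria for marked vital signs abnormalities, in the laboratory and quality appendix (16.1.10), state for pulse: "There is no grading scale for pulse rate".

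**The concern.** A safety shift table is meant to show participants moving between normal and abnormal after vaccination, by arm. These two shells show only movement among people already abnormal at both visits, and their footnotes restrict counts and percentages to participants with a response at both times.

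The trial's own design makes the missing category the usual starting point. Protocol 5.2 admits people who are healthy or medically stable. The eCRF attaches a vital-sign grade only to readings marked Abnormal CS. The Day 8 examination is driven by reported symptoms (SAP 17.6), so its findings may well arise in people with nothing recorded at screening. At stake is whether two outputs the SAP promises can show new findings by arm at all.

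**Working it through.** The plan gives no figure on this point to reproduce. The check is of table structure, followed by a search for other outputs that carry the same information.

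**1. Is the category really absent?** In Table 14.3.6.2 the grid and the legend agree on Grades 1 to 4. In Table 14.3.7.1 the grid has two categories and the note adds only a total column. Table 14.3.6.3 does carry Normal, and Listing 16.2.7.3 shows Grade 0 for temperature. The omission is therefore specific to these two shells and is not a loss in text extraction.

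**2. Cell counts, per arm and per parameter or body system:**

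| Table | Cells as drawn | Cells for a new abnormality | Cells for resolution |
|---|---|---|---|
| 14.3.6.2 | 4 × 4 = 16 | 0 | 0 |
| 14.3.7.1 | 2 × 2 = 4 | 0 | 0 |
| 14.3.6.3 | 3 × 3 = 9 | 2 (Normal to NCS, Normal to CS) | 2 (NCS to Normal, CS to Normal) |

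Adding one no-abnormality category to both axes gives:

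- 14.3.6.2: 5 × 5 = 25 cells. The 25 − 16 = 9 added are 4 new, 4 resolved and 1 unchanged.
- 14.3.7.1: 3 × 3 = 9 cells. The 9 − 4 = 5 added are 2 new, 2 resolved and 1 unchanged.

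**3. What other by-arm output holds a new examination finding?** For a CS finding after Day 1, the targeted examination form asks for an AE number. Such a finding should therefore reach the adverse event tables, which are by arm. The form asks for no such link for an NCS finding, and SAP 17.6 plans no other examination summary, so NCS findings appear only in Listing 16.2.8.3. No other table shows the shift itself.

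**4. What other by-arm output holds a new graded vital sign?** The eCRF, and the footnote to Listing 16.2.8.2 (the source for Table 14.3.6.2), give a grade only to Abnormal CS readings. A newly graded reading is therefore a newly CS reading, and Table 14.3.6.3 counts it under Normal to CS or NCS to CS. What is lost is the split by grade: new Grade 1 and new Grade 3 blood pressure, both judged CS, fall in the same cell. SAP 17.5 also names actual values and change by grade, but the shells contain no vital-signs table by grade other than 14.3.6.2.

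**5. Pulse rate.** The eCRF offers free text, not a grade, for a CS pulse finding, so the pulse section of Table 14.3.6.2 cannot be filled.

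**6. Can the missing category be derived?** Yes, with stated rules. Both examination forms record abnormal findings only, with no normal response per system. The Day 8 form asks whether the targeted examination was done and whether symptoms required evaluation, which separates examined from not examined. The pick-lists differ: screening has general appearance and musculoskeletal, and Day 8 has heart auscultation.

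**The case against.** The strongest reply is that little depends on these tables. Vital-sign and examination shifts are not among the four primary safety endpoints, and no hypothesis, sample size or licensure criterion uses them. Other outputs cover much of the ground. Table 14.3.6.1 gives actual values and change from baseline by arm, Table 14.3.6.3 gives shifts by clinical significance, and temperature on Days 1 to 7 is summarised by maximum severity as a solicited event. That stands, and it sets the size of the point.

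It also rules out a stronger reading. A reader might infer that an imbalance between vaccine and placebo in new findings would be visible only in listings, or that no table counts a new graded vital sign. The documents do not support either. CS examination findings at Day 8 are tied to an AE number, and a new graded vital sign is counted in Table 14.3.6.3. The listing-only description fits NCS examination findings alone.

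A second objection concerns the obvious remedy. One Normal category that also took in participants not examined would treat the unexamined as normal, while SAP 7.3 says missing safety data will not be imputed. That stands too, and the fix keeps the two apart.

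What the reply does not answer is that the two shells, followed as drawn, cannot deliver the shifts SAP 17.5 and 17.6 describe.

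**Conclusion.** The defect holds and is modest in size. Tables 14.3.6.2 and 14.3.7.1 have no cell for a participant without an abnormality at baseline or at Day 8, and the first asks for a grade that pulse rate does not have. The by-arm information lost is:

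- new NCS examination findings, and the examination shift itself;
- the grade split of new CS vital signs.

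These are descriptive safety outputs. The documents give no rates from which to say how many participants would be affected.

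The verdict rests on two assumptions. First, grades come from the eCRF as recorded, that is, for CS readings only. If grades were instead assigned from the measured values, a Grade 1 blood pressure judged NCS, which Protocol 9.1.3 allows at entry, could fill some baseline rows. The shell would still lack its no-abnormality category. Second, sites follow the form and enter an AE number for every CS finding at Day 8.

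**What to change.** **Table 14.3.6.2.** Add a Grade 0 / not graded row and column. Keep it separate from eCRF code 0, which means Ungradable. Drop pulse rate, which Table 14.3.6.3 already covers.

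**Table 14.3.7.1.** Add No abnormal finding recorded to both axes, and a separate Day 8 column for Exam not required / not done. The layout becomes 3 rows × 4 columns = 12 cells per arm and system. State in the SAP:

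- how the no-finding category is derived at each visit from the eCRF questions;
- how the screening and Day 8 body-system lists are mapped;
- that unexamined participants are not counted as normal, so percentages for the examined categories use those assessed at both visits.

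A footnote should say why the label is not Normal. The screening form's lead question asks only about CS findings, so an NCS finding left unrecorded at screening could look new at Day 8.

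The cost is some extra derivation and programming. No new data are needed.
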